7.2 Dose Determination

Doses of sorafenib will be determined by the phase of the study in which the patient is enrolled. Letrozole is given at a fixed dose of 2.5 mg daily for both the phase I and phase II portions of the study.

7.3 Treatment Administration

Treatment will require daily oral administration of medications on an outpatient basis.

Treatment may be delayed for up to two weeks for recovery from Grade 3 or 4 adverse events. If patients do not recover within two weeks, the patient will be removed from study.

7.3.1 Letrozole

Patients will take letrozole orally at a daily dose of 2.5 mg/day on Days 1 through 28.

Letrozole may be taken with or without food. Tablets should be swallowed whole with 8 ounces or 250 ml of water.

Patients will be provided with a Medication Diary for letrozole, instructed in its use, and asked to bring the diary with them to each appointment.

7.3.2 Sorafenib

Patients will also take sorafenib orally at a daily dose to be determined based upon the phase of the study that patient is enrolled (See Section 7.4). Sorafenib will be taken on Days 1 through 28.

Sorafenib should be taken on an empty stomach, at least 1 hour before or 2 hours after a meal. Tablets should be swallowed whole, not crushed or chewed, with 8 ounces or 250 ml of water. Sorafenib should not be taken with grapefruit juice.

Patients will be provided with a Medication Diary for sorafenib, instructed in its use, and asked to bring the diary with them to each appointment.

7.3.3 Missed Doses

If patients vomit after taking letrozole or sorafenib, patients should be instructed not to retake the dose. Patients should take the next scheduled dose of letrozole or sorafenib therapy.

If a scheduled dose is missed, patients should be instructed to take the dose as soon as remembered. If it is near the time of their next dose they should be instructed to skip the dose and resume their usual dosing schedule. Patients should not double their dose to catch up missed doses.

7.4 Phase I Dose Modifications or Escalations

7.4.1 Phase I Component

For the Phase I dose escalation portion of the trial, patients will be enrolled in two cohorts (Level 0 and 1) with the following dose escalation rules:

Dose Level 0

The first three patients will start at Level 0:

- If 0 patients experience dose-limiting toxicity (DLT) during cycle 1, the dose will be escalated to Level 1.
- If 1 of the first 3 patients experience DLT in cycle 1, we will expand the cohort and 3 more patients will be treated at Level 0 for a total of 6 patients.

Phase I/II Trial of Letrozole and Sorafenib as First-Line Therapy in Postmenopausal Women with Hormone Receptor-Positive Locally Advanced or Metastatic Breast Cancer PI:

 If 1 of these 6 patients experiences DLT in cycle 1, the dose will be escalated to Level 1.

If 2 or more of the patients in this cohort experience DLT in cycle 1, we will have
exceeded the maximum tolerated dose (MTD) and will de-escalate to Level -1 and
enroll 3 patients. If no patients experience DLT during cycle 1, this will be the
recommended phase II dose.

Dose Level 1

The second cohort of three patients will be started according to the rules above and enrolled as follows:

- If 0 patients experience DLT at Level 1 in cycle 1, this will be our recommended phase II dose.
- If 1 of the first 3 patients experience DLT in cycle 1, we will expand the cohort and 3 more patients will be treated at Level 1 for a total of 6 patients.
- If 1 of these 6 patients experiences DLT in cycle 1, this will be our recommended phase II dose.
- If 2 or more of the patients in this cohort experience DLT in cycle 1, we will have exceeded the MTD and Level 0 will be the recommended phase II dose.

Each of the two dose levels of sorafenib will be given with letrozole at 2.5 mg orally daily as outlined in the dose escalation schedule listed in the following table:

Does Escalation Schedule				
Dose Level	Dose of Sorafenib			
Level 1	400 mg po twice a day			
Level 0	400 mg po daily			
Level -1	400 mg po every other day			

Intrapatient dose escalation will be allowed for patients enrolled at Level 0 and if they do not experience DLT during Cycle 1, they can escalate to Level 1 for Cycle 2.

DLT will be evaluated in the first cycle of therapy and defined as: Grade 3 or 4 non-hematologic toxicity (except alopecia, nausea, emesis that resolves to ≤ Grade 1 with symptomatic treatment) or Grade 4 hematologic toxicity that is thought to be related to sorafenib.

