16.1 Primary and Secondary Hypotheses

The study will require a short run-in phase I portion to determine the recommended phase II dose. The primary objective of the single arm single-stage phase II portion of the study is to determine the clinical benefit rate (proportion of patients who achieve a complete response, partial response, or stable disease ≥ 6 months) of letrozole and sorafenib as first-line therapy in postmenopausal women with hormone receptor-positive locally advanced or metastatic breast cancer. The secondary objectives are to determine the safety and tolerability of sorafenib in combination with letrozole and evaluate time to progression and overall survival.

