16.2 Sample Size Justification

A historical study showed that single-agent letrozole in the first-line treatment of patients with hormone receptor-positive metastatic breast cancer had a clinical benefit rate of 50% compared to tamoxifen. The combination therapy of letrozole and sorafenib will not be considered of further interest if the true clinical benefit rate is less than or equal to 50%. We assume that this study will target a clinical benefit rate of 67% for identifying the combination therapy as active and worthy of further investigation. With these settings, the null hypothesis is that the clinical benefit rate of the combination therapy is less than or equal to 50%, and the alternative hypothesis is that the clinical benefit rate of 67% or more is of considerable interest. For the phase II part of the study, the sample size was calculated according to a single-stage design. The study will accrue a total of 58 patients, and the combination therapy will be accepted if there are at least 35 responders out of 58 patients. The design will have a 4.3% (< 5%) type-I error (false positive) rate and a power of 82.7% (> 80%) (i.e., 17.3% type-II error or false negative rate). The total number of evaluable patients to be accrued to this study is not expected to exceed 64 patients.

Phase I/II Trial of Letrozole (and Sorafenib as First-Line Therapy in Postmenopausal Women with Hormone Receptor-Positive Locally Advanced or Metastatic Breast Cancer PI:

The patients accrued in the Phase I dose escalation will be included in the Phase II portion if they receive the same dose. Evaluable patients for the phase I portion are defined as study-eligible patients who have received at least one cycle of treatment. Evaluable patients for the phase II portion are those who have received at least two cycles of treatment.

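### The phase II dose can be named on three women, and the supplied protocol states no study-level toxicity count that would hold accrual afterwards

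*Combined protocol and SAP*

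**What the plan says.** Section 7.4.1 uses cohorts of three, expanded to six only when one of the first three has a DLT.

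- **Level 1, no DLT in three:** "If 0 patients experience DLT at Level 1 in cycle 1, this will be our recommended phase II dose".
- **Level 1, one DLT in three:** "3 more patients will be treated at Level 1 for a total of 6 patients", and then "If 1 of these 6 patients experiences DLT in cycle 1, this will be our recommended phase II dose".
- **Level 1, two or more DLTs:** "we will have exceeded the MTD and Level 0 will be the recommended phase II dose". Level 0 may itself have been cleared on 0/3.
- **Level -1:** three women are enrolled, and the only outcome with an action is the clean one: "If no patients experience DLT during cycle 1, this will be the" recommended phase II dose.

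The DLT window is one cycle: "DLT will be evaluated in the first cycle of therapy and defined as". Section 7.5.1 then describes phase II as given at the MTD.

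Section 16.1 sets the next step: "The primary objective of the single arm single-stage phase II portion of the study" is to determine the clinical benefit rate. Section 16.2 accrues 58 patients and judges the combination on a count of responders. It also says: "The patients accrued in the Phase I dose escalation will be included in the Phase II portion if they receive the same dose". Phase II evaluability requires at least two cycles of treatment.

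The toxicity provisions after dose selection are:

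- modification and discontinuation rules for the individual patient (7.5.2);
- toxicity assessment before each cycle and event reporting (Section 8);
- individual off-study criteria (Section 10);
- monitoring and audits under an external DSMP (Section 14);
- a descriptive summary of serious adverse events (16.4).

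**The concern.** The recommended phase II dose is primary objective 1.1.1, and safety and tolerability are a secondary objective. A dose that passes on 0/3 has been tested against the protocol's MTD criterion with the smallest possible sample. From then on the only study-level count with a consequence is the efficacy count at 58. Two or more DLTs in a phase I cohort would have ruled Level 1 out. The same number among the next women enrolled after a 0/3 start triggers nothing in the supplied text.

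The primary result may not show the problem either. Women who stop before completing two cycles are not evaluable for phase II, so early toxicity can leave the denominator. If those women are replaced, more than 58 may be treated.

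**Working it through.** **The plan's own figures.** The protocol gives no target DLT rate and no operating characteristics for the dose rule, so there is no stated toxicity figure to reproduce. The error rates in 16.2 concern efficacy only, and nothing below uses them. (Separately, an exact binomial calculation for at least 35 of 58 gives a type I error of 7.4% and power of 88.7%. The stated 4.3% and 82.7% correspond to at least 36.)

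**Inputs.** The 0/3 and 1/6 acceptance rules come from 7.4.1. The accrual of 58, with phase I women at the same dose included, comes from 16.2. The true cycle-1 DLT rate p is assumed, and 20% to 50% is shown.

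**Step 1: women still to enter.** After 0/3, 58 - 3 = 55. After 1/6, 58 - 6 = 52.

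**Step 2: what 0/3 rules out.** The exact one-sided 95% upper limit is 1 - 0.05^(1/3) = 63.2%.

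**Step 3: chance that the rule accepts the level, given that it is reached.** P(accept) = (1-p)^3 + 3p(1-p)^2 × (1-p)^3.

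| Assumed p | by 0/3 | by 1/6 | total |
|---|---|---|---|
| 20% | 51.2% | 19.7% | 70.9% |
| 30% | 34.3% | 15.1% | 49.4% |
| 40% | 21.6% | 9.3% | 30.9% |
| 50% | 12.5% | 4.7% | 17.2% |

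At these rates about 70% of acceptances rest on three women. The figures are conditional on reaching Level 1. With an assumed 20% at Level 0 and 40% at Level 1, the unconditional chance is 0.709 × 0.309 = 21.9%, and 0.709 × 0.216 = 15.3% on three women.

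**Step 4: expected DLTs afterwards.** Among 55 further women treated at the dose: 55 × 0.40 = 22.0, or 55 × 0.50 = 27.5. No stated count responds to these.

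**Step 5: what a continued tally could do (illustration only).** Suppose enrolment is held at 3 or more DLTs in 6 women, 5 or more in 12, or 9 or more in 24, counting phase I women at that dose. An exact recursion from the 0/3 and 1/6 starting points gives:

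| Assumed p | accepted | accepted and never paused | paused, among accepted |
|---|---|---|---|
| 20% | 70.9% | 68.5% | 3.3% |
| 30% | 49.4% | 40.0% | 19% |
| 40% | 30.9% | 15.1% | 51% |
| 50% | 17.2% | 3.1% | 82% |

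The last column is 1 minus the third column divided by the second.

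**Step 6: Level -1.** Any DLT among the three women reaches an outcome with no stated action. If p there were 20%, that is 1 - 0.8^3 = 48.8% of Level -1 cohorts. This is conditional on Level 0 having failed. With 20% at both levels it is (1 - 0.709) × 0.488 = 14.2% of all trials.

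**The case against.** The strongest reply is that 0/3 is not the only evidence. Level 1 is 400 mg twice daily, which Section 2.1.3.2 reports as already given alone to 299 patients with hepatocellular carcinoma and in two breast cancer phase II trials. The 54-patient trial had one grade 4 drug-related event. Section 7.7 cites permanent discontinuation in 3 of 451 patients for hand-foot reaction and 1 of 451 for hypertension, and Section 2.1.5 expects no pharmacokinetic interaction. This stands as a reason not to treat 40% or 50% as likely. It does not show what the combination does, which is what the phase I portion is for. A cohort of three at the top planned level is a conventional design choice and is not the fault here.

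Three stronger readings are tempting, and the documents do not support them.

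- **That the trial cannot notice excess toxicity.** Toxicity is assessed before every cycle, serious events are reported within 24 hours, and study status is monitored centrally. What is missing from the supplied text is a numeric trigger.
- **That no stopping rule exists anywhere.** The DSMP is not supplied and Section 14 is incomplete.
- **That early toxicity stops must lower the clinical benefit rate.** Under the two-cycle evaluability rule such women may leave the denominator. A DLT is also not necessarily a stop, since Table 7.5.2.2 allows treatment to resume after a first grade 3 event.

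The illustrative boundary has real weaknesses. It pauses 19% of accepted runs at a 30% rate, lets 49% of accepted runs at 40% reach 58 unpaused, and has no look after 24. It also lets 2 of 6 continue, a count that 7.4.1 treats as exceeding the MTD. It shows that a tally has value but is not a rule to adopt as it stands. Individual dose reductions lessen exposure but do not stop enrolment.

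**Conclusion.** The point holds in this form: the phase II dose can be fixed on three women, up to 55 more evaluable women follow in one stage, and the supplied text neither retests the dose against the protocol's own MTD criterion nor states a count that would hold accrual. If a level with a true cycle-1 DLT rate of 40% or 50% is reached, it is accepted 30.9% or 17.2% of the time. Those rates are assumptions, and the figures are conditional on reaching the level. The absence of a rule is established only for the supplied text. The gap in the Level -1 branch is plain on the page and needs no assumption. This should be corrected because it bears on a primary objective and the data needed are already collected.

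**What to change.** In 7.5.1 and Section 16, reconcile phase II with the phase I criterion:

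1. Keep tallying cycle-1 DLTs, under the 7.4.1 definition, in every woman treated at the recommended dose. Count phase I and phase II together, whether or not the woman is evaluable for efficacy.
2. Prespecify a statistical boundary across the whole of accrual that holds new enrolment for review under the DSMP. If the DSMP already contains such a rule, cite it instead.
3. Have the sponsor choose the boundary and report its operating characteristics over a range of true rates, including the chance of an unneeded pause.
4. Reconcile the Level -1 branch so that every outcome in its three women has a stated action.

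No dose or clinical rule is proposed; what follows a hold is for the review to decide.

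The cost is a protocol paragraph plus DLT adjudication (attribution to sorafenib and the symptomatic-treatment exceptions) for phase II women, whose toxicity is already recorded. Each look may need a wait for cycle 1 to finish, or must accept some overrun. Unneeded pauses depend on the boundary: in the illustration, 3.3% of accepted runs at a 20% rate and 19% at 30%. The tally itself adds no patients.

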7.1 General Considerations

Treatment will be administered on an outpatient basis. Patients will be instructed to start study drugs on Day 1 of each 28-day treatment period. One cycle is defined as 28 days of treatment. Prior to starting a cycle, all patients must continue to meet all inclusion criteria (see Section 5.1). No investigational or commercial agents or therapies other than those described below may be administered with the intent to treat the patient's malignancy. Patients will receive treatment until it is no longer of benefit to them. Patients may discontinue therapy at any time for any reason.

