7.8 Adherence/Compliance

Patient compliance in daily self-administration of the oral tablets will be assessed at each clinic visit. Patients will be given a medication diary and instructed to fill out how many tablets (letrozole and sorafenib) were taken each day and the time of day the drug was taken. At the end of each cycle of treatment, the actual amount of unused drug will be compared to the anticipated amount of unused drug and the patient's medication diary.

8. Toxicity Monitoring and Adverse Event Reporting

All patients who receive one dose of protocol therapy will be evaluable for assessment of toxicity. Prior to each cycle the treating physician will fully assess the patient's condition with respect to possible treatment related toxicities. All adverse events, whether observed by the physician or reported by the patient, occurring during the active portion of therapy, or up to 30 days after the last dose of treatment will be graded by a numerical score according to the NCI's Common Terminology Criteria for Adverse Events (CTCAE), Version 3.0 (http://ctep.cancer.gov/reporting/ctc.html) and recorded in the patient's medical record.

Phase I/II Trial of Letrozole (and Sorafenib as First-Line Therapy in Post Women with Hormone Receptor-Positive Locally Advanced or Metastatic Breast Cancer	menop	ausa
PI:		

Adverse events will be recorded on electronic case report forms in accordance with a study-specific data capture plan.

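### Section 7.4.1 lets a DLT-free Level 0 patient double her sorafenib dose for Cycle 2 without requiring that the Level 0 cohort has been cleared

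*Combined protocol and SAP*

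**What the plan says.** Section 7.4.1 has two rules for reaching Level 1.

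The cohort rule governs new patients and depends on Cycle 1 of the Level 0 group:
- No DLT in three: "If 0 patients experience dose-limiting toxicity (DLT) during cycle 1, the dose will be escalated to Level 1".
- One DLT in three: "we will expand the cohort and 3 more patients will be treated at Level 0 for a total of 6 patients".
- One DLT in six: "If 1 of these 6 patients experiences DLT in cycle 1, the dose will be escalated to Level 1".
- Two or more DLTs: the trial has "exceeded the maximum tolerated dose (MTD) and will de-escalate to Level -1 and" enrols three patients there.

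The intrapatient rule governs patients already at Level 0: "if they do not experience DLT during Cycle 1, they can escalate to Level 1 for Cycle 2". Its only condition is the patient's own Cycle 1.

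DLT is assessed in the first cycle only. The dose table gives 400 mg once a day at Level 0 and 400 mg twice a day at Level 1.

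**The concern.** The phase I part exists to find out whether sorafenib is tolerable with letrozole, starting at half the usual single-agent daily dose. One DLT in three is the result on which the protocol says it cannot yet decide about Level 0. At that point the intrapatient rule still allows the two unaffected patients to take twice the dose in question.

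Little would be learned in return. Toxicity in a patient escalated at Cycle 2 falls outside the DLT window, so it would not enter the formal Level 1 decision. Nor does a clean first cycle settle the matter for the individual: Section 7.7 says rash and hand-foot reaction tend to emerge over the first six weeks, which is longer than the 28-day window.

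**Working it through.** **1. Dose step.** Level 0 is 400 mg/day. Level 1 is 2 × 400 = 800 mg/day. The ratio is 800/400 = 2.

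**2. Is a cohort condition supplied elsewhere?** The other provisions that bear on dosing are:
- Section 7.1: "Prior to starting a cycle, all patients must continue to meet all inclusion criteria". This is an individual check.
- Section 7.3: "Treatment may be delayed for up to two weeks for recovery from Grade 3 or 4 adverse events". This is an individual check.
- Section 7.5.2 tables: hold, reduce or stop according to the patient's own toxicity. They sit under a phase II heading, so their reach into phase I is arguable.
- Section 8: the physician assesses each patient for toxicity before each cycle.
- Section 10: withdrawal for the patient's own life-threatening drug-related toxicity.
- Section 17.1: general oversight of the study and of patient data, with no dose rule attached.

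None makes an individual's escalation depend on the cohort result.

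**3. Timing.** The 1-of-3 result is known once all three patients have finished Cycle 1. The three expansion patients then need their own 28-day Cycle 1. Escalation is tied to Cycle 2, so the two DLT-free patients would normally become eligible before the expansion result exists.

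**4. How often.** The plan states no figure to reproduce and no DLT rate under its own definition, so the Level 0 rate p is an assumption. Let q = 1 − p, with patients independent.
- Expansion state (1 of 3, two DLT-free patients eligible): 3pq²
- Level 0 later fails, given expansion: 1 − q³
- Level 0 fails after expansion, of all trials: 3pq²(1 − q³)
- 2 of 3 DLTs (one DLT-free patient): 3p²q

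At p = 0.05: 3 × 0.05 × 0.95² = 0.135. At p = 0.10: 3 × 0.10 × 0.90² = 0.243.

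| Assumed p | Expansion state | Later failure, given expansion | Failure after expansion, all trials | 2 of 3 DLTs |
|---|---|---|---|---|
| 5% | 13.5% | 14.3% | 1.9% | 0.7% |
| 10% | 24.3% | 27.1% | 6.6% | 2.7% |
| 20% | 38.4% | 48.8% | 18.7% | 9.6% |
| 30% | 44.1% | 65.7% | 29.0% | 18.9% |

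The fourth column is a subset of the second. Section 2.1.3.2 (one grade 4 drug-related event among 54 single-agent patients) and Section 17.2 (grade 3 and 4 reactions described as uncommon) point towards the upper rows, as direction only. Nothing in the documents supports 20% or 30%; those rows show sensitivity. Every figure counts eligibility for an optional step, not escalations made or harm done.

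**5. With a cohort gate.** No patient could move to Level 1 from an uncleared or failed Level 0 cohort, so the eligible number in the expansion state falls from two to zero.

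**The case against.** The best defence is that the two rules answer different questions. The cohort rule picks the dose for new patients and for phase II. The intrapatient rule adjusts the dose of a woman who has herself tolerated 28 days of treatment. The wording is permissive, so an investigator may decline.

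Level 1 is also not a novel dose. It was the single-agent dose in both breast cancer studies and in the 299 sorafenib patients of the hepatocellular trial (Section 2.1.3.2). Section 7.7 reports permanent discontinuation for hand-foot reaction in 3 of 451 patients and for hypertension in 1 of 451, and asks for weekly blood pressure over six weeks, which reaches into Cycle 2. Section 2.1.5 expects no pharmacokinetic interaction. At 5% and 10%, an expanded Level 0 would go on to clear in 85.7% and 72.9% of cases (1 − 0.143 and 1 − 0.271).

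Most of this stands, and it keeps the point small. It does not supply the missing condition. The cited experience is with sorafenib without letrozole, and Section 2.1.5 forgoes detailed pharmacokinetics while providing the short phase I part, so the cohort rule is the main planned check on the combination. In the expansion state, one of three patients has already had a DLT at the lower dose, which weakens general reassurance. Optional wording leaves a cohort-level question to each investigator.

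A reader might infer something stronger: that the protocol endorses doubling the dose after 2 or more DLTs have put Level 0 above the MTD. The documents do not support that. Section 7.4.1 then directs de-escalation to Level -1, which can fairly be read as overriding an optional step. The text does not say which rule prevails, so this is an ambiguity and no more.

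**Conclusion.** The gap is real and modest. As written, Section 7.4.1 permits two DLT-free patients to go to 800 mg/day after 1 of 3 DLTs, while 400 mg/day with letrozole is still under test. That state arises in 13.5% to 24.3% of trials if the Level 0 DLT rate is 5% to 10%, and more often above that. The reading of the rule does not depend on these rates; only its frequency does.

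A reader might also infer that patients face an untested dose or that the phase II result is compromised. Neither follows. Level 1 is the established single-agent dose, individual toxicity checks remain in force, and the primary test of clinical benefit in 58 patients is unaffected. This is a safety rule that should be brought into line with the cohort rule beside it.

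**What to change.** Replace the intrapatient sentence in Section 7.4.1 with:

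> A patient enrolled at Level 0 who has no DLT in cycle 1 may escalate to Level 1 at the start of a later cycle only after the Level 0 cohort has been cleared (0 of 3 or 1 of 6 patients with DLT in cycle 1), and only while Level 1 has not been found to exceed the MTD. No Level 0 patient may escalate if 2 or more DLTs occur at Level 0.

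The condition on Level 1 is needed because patients who wait may become eligible after Level 1 results are in. The last sentence removes the ambiguity about 2 or more DLTs.

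The cost is that some DLT-free patients stay at Level 0 for a cycle or more. Section 16.2 counts phase I patients in phase II if they received the same dose, and requires two cycles for evaluability, so the delay may slightly change which phase I patients count. The planned sample size and the primary test stay as they are.
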